increase DRS	regularly have their eyes	at CCHC.	observation
attendance in	screened.		period.
participants living			
with diabetes,			
compared to not			
sending a			
reminder.			

Secondary Objectives

Objective Brief Description/Justification o Outcome Measure		Outcome Measured By	Time Frame
Assess whether linguistically tailored reminders incorporating BCTs increase DRS appointment bookings in participants living with diabetes, compared to not sending a reminder.	Not all participants who book an appointment may attend an appointment. Assessing appointment booking in addition to appointment attendance is important to understand if the intervention is effective in both promoting appointment booking and attendance.	The proportion of participants in each condition who book a DRS appointment at CCHC.	Assessed at the conclusion of the intervention/ observation period.
To examine whether the effect of the intervention on DRS attendance is moderated by participant characteristics, including age, gender/sex, preferred language, prior DRS attendance, and Forward Sortation Area (FSA).	Participant characteristics are likely to influence appointment booking and attendance.	Interaction effects between intervention group and subgroup variables (age, gender/sex, preferred language, prior DRS attendance, FSA) in a logistic regression model predicting DRS attendance.	Assessed at the conclusion of the active intervention period (4 months after first wave of reminders is sent).

Study Design and Endpoints

Description of Study Design

This study is a two-arm randomized controlled trial (RCT) evaluating the effectiveness of a linguistically tailored, BCT based electronic reminder in promoting diabetic retinopathy screening (DRS) attendance. Participants will be randomly assigned to one of two study arms:

- Control group (no reminder)
- Reminder Group (receives reminder incorporating knowledge, social and goal based BCTS).

Participants will be drawn from the Community Diabetes Education Program of Ottawa (CDEPO), registered at Centretown Community Health Centre (CCHC). To avoid overloading clinic resources, reminders will be sent in two waves. Control group participants will be matched to these waves based on distribution timing.

Duration of Study Participation

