hosted by TELUS Health Solutions Inc.) will be identified by CCHC staff. Three hundred and thirty of those eligible will be randomly selected to participate in the study and automatically enrolled.

Participant Inclusion Criteria

Individuals are eligible to participate in the study if they:

- a) Are registered to the CDEPO program at CCHC, and
- b) have T1DM or T2DM, and
- c) have consented to virtual communications from CCHC (as indicated by the inclusion of their email address in the CCHC EMR), and
- d) are 18 years of age or older
- e) have an active chart (i.e., chart has been updated within the last two years, and
- f) have not already attended a DRS appointment with DESO (as indicated in the individual's EMR).

Participant Exclusion Criteria

Individuals are ineligible to participate in this study if they:

- a) Are not registered to the CDEPO program at CCHC, or
- b) are registered in CDEPO at CCHC but do not:
 - o have T1DM or T2DM, or
 - have not consented to virtual communications from CCHC (as indicated by an email address not being listed in the client's EMR), or
 - o are not 18 years of age or older
 - o Do not have a chart that has a been active in the last two years, or
 - have already attended a DR screening appointment with DESO (as indicated in chart).

Strategies for Recruitment and Retention

As contacting participants in advance would introduce bias, consent for trial participation will be waived. Participants will be debriefed after the trial concludes, either in person or by email, depending on their engagement with the DRS appointment process. Those who attend a DRS appointment will be debriefed in person at CCHC in the eye screening room upon arrival. Those who do not attend will receive a post-study debrief via email, using the OCEAN platform.

Given the passive nature of participation—limited to receiving a reminder and the option to attend a routine DRS appointment—no additional recruitment or retention strategies are necessary.

Participant Withdrawal or Termination

Reasons for Withdrawal or Termination

Participants are free to withdraw from the study at any time upon request. An investigator may terminate participation in the study if:

- An investigator determines continued participation is not in the participant's best interest.
- The study is discontinued.
- The Ottawa Health Science Network Research Ethics Board (OHSN-REB) withdraws study approval.

Handling of Participant Withdrawals or Termination

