- No data will be transferred to the research team until at least two weeks after all participants have been debriefed. Until then, follow-up data (e.g., booking or attendance status, withdrawal requests) may continue to be documented by CCHC staff to ensure complete and accurate records.

Study Procedures / Evaluations

Procedures/Evaluations

When a participant books or attends a DRS appointment, DESO staff will update the DESO Reminder Trial Tracker, which will be maintained within the EMR system (see example below).

Example Remine	der Trial Tracker:
Reminder Received?	Appointment with DESO Booked
Client Contacted DESO Date (DD/MM/YY)	□ Yes □ No
Client Contact Type	□ In process
 Phone call 	If appointment booked- interpretation services booked?
 Email 	□ Yes
 Self-Referral Form Online 	□ No
 No contact (default) 	Appointment Attended?
Language Spoken by Client	□ Yes □ No show
Age of client in years Forward Sortation Area (first 3 digits of postal code):	Retinopathy Status:
Has client had a DRS exam before?	Contacted to withdraw data from study?
□ Yes	 No (default)
□ No	 Yes (if yes, DO NOT include this participant's data
If yes, approximately what year was last DRS exam	in the data pull)

After the debriefing period, CCHC staff will extract de-identified trial data and transfer it as a CSV file to a secure OHRI SharePoint folder accessible only to the approved research team. Variables shared with the research team will include all information logged in the Reminder Trial Tracker. The research team will also be advised of the number of participant withdrawals from each group.

Pt ID	Arm	Wave	Contact Clinic (Y/N)	Book Appointm ent (Y/N)	Attend Appoint ment (Y/N)	Age	Gender	Sex	Prior DRS	Spoken Langua ge	DR Status	FSA
1												
2												

Example csv data file.

[figure not shown]
Control of Bias and Confounding

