interpretation booked,	arm.		secure SharePoint	
appointment attended,			file between OHRI	
retinopathy detected, spoken			and CCHC.	
language, age, FSA, prior DRS				
attendance.				
Web analytics (basic metrics	To describe website use	Google	Data will be	JP. JO,
including number of website	as this is the platform for	analytics or	exported to a	MD. EG
visits, duration of website	the intervention.	website	secure SharePoint	
visit/ session. clicks on		developer	by the Site Owner	
secondary link) No web		analytics	(CCHC)	
identifiers (e.g., IP address				
are to be collected)				

Data Collection and Management Responsibilities

De-identified quantitative data will be collected as part of the reminder evaluation. Only the variables specified in the Reminder Trial Tracker will be collected. Final data collection at the site level may continue beyond the active intervention period to allow documentation of any appointments or withdrawal requests that occur before participants are debriefed. This data will be stored in CSV format on a secure OHRI SharePoint site with access limited to study team members responsible for the analysis.

Data Sharing and Reuse

Identifiable data will not be shared. Summaries of analysed data may be shared with relevant partners (i.e., CCHC, Diabetes Action Canada, OHRI research team meetings) prior to the submission of final reports or manuscripts.

De-identified and cleaned datasets, with all direct and indirect identifiers removed, may be uploaded to a secure open-access repository such as the Federated Research Data Repository (FRDR). FRDR is a national platform designed to support the sharing and preservation of Canadian research data.

Study Records Retention

Raw data, data summaries and analyzed data will be stored in a secure file within SharePoint that can only be accessed restricted to members of the study team. Should a researcher leave before the end of the data retention (i.e., 10 years post study completion), they will be removed from the shared folder. JP is responsible for any questions during the retention period.

Protocol Deviations

Any need to deviate from the approved protocol will be reported to the REB and no changes will be made to the approved protocol without informing the REB.

Knowledge Translation

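### Gender/sex is a planned moderator but is absent from the only variable set to be collected, and no source is given for the moderators of participants who never contact the clinic

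*Protocol*

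**What the plan says.** **Moderators.** The second secondary objective (Protocol, Secondary Objectives) is measured by "Interaction effects between intervention group and subgroup variables (age, gender/sex, preferred language, prior DRS attendance, FSA") in a logistic model for attendance. Statistical Methods repeats the five variables, calls the fourth a prior DRS record, and applies intention to treat to all analyses.

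**Tracker.** Under Procedures/Evaluations, "When a participant books or attends a DRS appointment, DESO staff will update the DESO Reminder Trial Tracker". The example tracker has fields for "Language Spoken by Client", for "Age of client in years Forward Sortation Area (first 3 digits of postal code"), and for "Has client had a DRS exam before", the last with an approximate year if yes. It has no field for sex or gender. The contact field is preset to "No contact (default").

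**What reaches the analysts.** Data Collection and Management Responsibilities states that "Only the variables specified in the Reminder Trial Tracker will be collected". The Data Management Plan table lists the tracker variables, including spoken language, age, FSA and prior DRS but not sex or gender, and names the EMR as the capture system. The example CSV under Procedures/Evaluations has separate columns for gender and sex.

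**Day 0.** Control of Bias and Confounding describes the file that CCHC sends for randomisation as holding the ID codes of eligible clients. The randomisation schedule asks that the arms be balanced on age and date of last chart update.

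**Eligibility.** Inclusion criterion (f) requires that participants "have not already attended a DRS appointment with DESO".

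**The concern.** There are two separate problems.

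First, the variable lists cannot all be right. If only tracker variables are collected and the tracker has no sex or gender, that moderator cannot be analysed and those CSV columns cannot be filled.

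Second, a moderator must be known for everyone randomised, and its value must not depend on what happened after randomisation. The stated trigger for entering trial data is booking or attending. If a moderator is obtained at that point, it is missing chiefly for people who did not respond, and the reminder is meant to change who responds. An interaction model fitted to those with a recorded value would then compare arms within a subset that the intervention itself selects. It would not estimate the moderation of the effect on attendance among all randomised, and it would conflict with intention to treat.

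**Working it through.** The protocol states no figure on this point, so there is none to reproduce. The check sets the passages side by side and then sizes the conditional worst case.

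**Step 1. Each moderator against each list**

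| Moderator | Example tracker | Data Management Plan list | Example CSV |
|---|---|---|---|
| Age | yes | yes | yes |
| Gender/sex | no | no | yes (two columns) |
| Preferred language | spoken language | spoken language | spoken language |
| Prior DRS | yes, with approximate year | yes | yes |
| FSA | yes | yes | yes |

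Gender/sex fails against the tracker-only rule. Language is present under a different definition. The one place where the protocol describes a preferred language being chosen is the reminder's landing page (Intervention Phase), which controls do not receive during observation.

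**Step 2. Which moderators could depend on contact**

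- Age and FSA: ordinary chart data, and age is needed at randomisation for balancing. Low risk.
- Prior DRS: criterion (f) removes anyone already screened by DESO, so a yes must mean screening elsewhere. An approximate year suggests recall, whereas Statistical Methods speaks of a record. The source is unsettled.
- Language: spoken or preferred, with no stated source for people who never call.
- Pre-set values: only contact status and withdrawal carry a default. An untouched tracker therefore shows that there was no contact, but gives no moderator values.

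**Step 3. Size if moderators were filled in only at booking or attendance**

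Inputs: 165 per arm and attendance of 0.03 (control) and 0.13 (intervention), from Total Number of Participants and Sites. The show rate (attended ÷ booked) is not given. I assume 60% to 90%, the same in both arms.

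Expected attendees = 165 × rate:
- Control: 165 × 0.03 = 4.95
- Intervention: 165 × 0.13 = 21.45
- Total: 26.4; 26.4/330 = 8.0%

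Expected bookers = attendees ÷ show rate:

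| Show rate | Control | Intervention | Total | Share of 330 |
|---|---|---|---|---|
| 60% | 8.2 | 35.8 | 44.0 | 13.3% |
| 70% | 7.1 | 30.6 | 37.7 | 11.4% |
| 80% | 6.2 | 26.8 | 33.0 | 10.0% |
| 90% | 5.5 | 23.8 | 29.3 | 8.9% |

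By arm, recorded moderators would cover 0.03/0.9 = 3.3% to 0.03/0.6 = 5.0% of controls, against 0.13/0.9 = 14.4% to 0.13/0.6 = 21.7% of the intervention arm.

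**Step 4. What a complete-case model would then estimate**

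Over all randomised, the design odds ratio is (0.13/0.87) ÷ (0.03/0.97) = 4.83. Among bookers with equal show rates in both arms it is 1.0, because the reminder's effect on booking has been conditioned away. Among attendees alone the outcome does not vary, so no model can be fitted.

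**The case against.** The strongest reply is that the protocol never says the tracker is completed only at booking or attendance. Much of the text points to data on everyone. The contact field has a no-contact default. The EMR is named as the source. Arms are to be balanced on age. Characteristics of those who neither book nor attend are to be described, and all analyses are by intention to treat. The tracker is labelled an example, and the CSV shows that sex and gender are wanted. The source and handling of covariates are often left to a statistical analysis plan, and the moderation analysis is described in the synopsis as exploratory.

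Most of this stands. It shows that data on all 330 are intended, and it makes age and FSA very likely available. It does not say how or when prior DRS and language are obtained for people who never make contact, and a Day 0 file described only as ID codes does not supply them. Nor does it remove the sex/gender contradiction, which lies within the protocol itself.

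A reader might also infer that prior DRS can only be self-report, or that nearly everyone with a recorded moderator would have attended. Neither is supported. Statistical Methods refers to a record, and chart-noted screening outside DESO can still vary. On the second, if bookings were 1.5 times attendances, 26.4/39.6 = 67% of bookers would attend.

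**Conclusion.** The contradiction over gender/sex is established from the text and needs no assumption. The second part is a gap in the protocol: no source or time point is stated for the moderators of participants who never make contact. The resulting risk of outcome-dependent capture is real for prior DRS and language, and slight for age and FSA.

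It would go too far to conclude that the moderation analysis will condition on the outcome, or that about 90% of moderator values will be missing. The coverage of 8% at attendance, or 9% to 13% at booking, is a worst case. It holds only if moderators are entered at those events alone, and the booking range also rests on the assumed show rate of 60% to 90%. Strictly, the conditioning would be on booking (itself a secondary outcome) or on attendance.

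The primary comparison of attendance and the comparison of bookings use no moderators and are unaffected. The point should be settled before reminders go out, because a baseline value obtained only by asking cannot be recovered later on equal terms in both arms.

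**What to change.** - At Day 0, before any reminder is sent, CCHC extracts age, sex, gender, chart-recorded language, FSA and chart-recorded DRS outside DESO from the EMR for all 330.
- State that the moderation models use only these baseline values.
- Add sex and gender to the tracker and to the Data Management Plan list, so that both agree with the CSV and the tracker-only rule.
- Use one definition of language, preferred or spoken, in the objective, tracker, CSV and Statistical Methods.
- Define prior DRS by its chart source. Drop it as a moderator if the EMR does not hold it for both arms.
- Use self-reports taken at contact only to describe attendees.

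The cost is one extra EMR export by the CCHC data manager, who already prepares the eligibility file, and a small amendment notified to the REB.

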We will use random number generation to assign a condition (control or reminder) to a client at the CCHC. Specifically, the CCHC member responsible for data management will share a CSV file containing unique client ID codes of all eligible individuals. Then the OHRI statistician (MT, BY) will conduct the randomization schedule below, through creating a randomized list of eligible individuals in a spreadsheet containing unique participants IDs. Once the file is prepared, the statistician will lock columns in the document to prevent errors and send the locked document to the CCHC. The document will be stored in an encrypted, limited access folder on the CCHC network. The unlocked columns of the spreadsheet will be used to track whether the client responded to the reminder and other study variables (see below for example spreadsheet). When the data is sent to the OHRI post-

trial, the client ID column will be removed and replaced by "Participant 1- ..." before sharing to clear the document of direct identifiers.

RANDOMIZATION SCHEDULE

- 1) 330 participants randomly selected from all eligible individuals listed in the Community Diabetes Education Program of Ottawa (CDEPO), registered at Centretown Community Health Centre (CCHC).
- 2a) 330 eligible participants randomly assigned to control (n = 165) or intervention (n = 165)
- 2b) Participants control and intervention groups should be balanced across age and date of last chart update
- 3a) Control group randomised into wave 1 and wave 2 (n= 80; 81)
- 3b) Intervention group randomised into wave 1 and wave 2 (n= 80; 81)

Statistical Considerations

Study Hypotheses

- Linguistically tailored reminders will significantly increase DRS appointment attendance (primary outcome) compared to no reminder.
- Linguistically tailored reminders will significantly increase DRS appointment booking compared to no reminder.

Sample Size Determination

Sample size calculations are based on a minimum effect estimate of 10% (based on the effective sizes usually detected in DRS trials¹⁸) and to achieve 80% power, which requires a total sample of 250 participants. To achieve this sample size, we have estimated we will need to randomize 330

individuals registered to the CDEPO program at CCHC to account for approximately 30% attrition due to outdated contact details or death.

Statistical Methods

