All analyses will be conducted according to the intention to treat principle. Descriptive statistics (mean and SD for continuous variables or median and IQR for skewed distributions, and frequency and proportion for categorical variables) will be used to summarize participant characteristics in each arm. For the primary analysis of the primary outcome, we will compare screening attendance between the arms using absolute and relative difference between two proportions with 95% confidence intervals and assess the statistical significance of the difference using a chi-squared test. If the large-sample assumptions are not met, Fisher's exact test will be used. Statistical significance will be assessed at the 5% level. A similar statistical approach will be used for secondary outcomes. For the final objective of assessing effect modification, we will use logistic regression analysis with the treatment arm, effect modifier and the interaction between treatment arm and effect modifier in the model. Least square mean differences from the model will be used to compare the outcome differences between the subgroup variables: 1) Age, 2) Gender/Sex 3) Preferred Language, 4) Prior DRS Record 5) FSA (Forward Sortation Area).

Source Documents and Access to Source Data / Documents

Access to study records will be limited to REB-approved members of the study team. The PI will permit study-related monitoring, audits, and inspections by the REB and/or OHRI and compliance and Version date: 04/06/2025

quality assurance groups of all study related documents (e.g. source documents, data collection instruments, study data etc.). The PI will ensure the capability for inspections of applicable study-related facilities (e.g. pharmacy, diagnostic laboratory, etc.). Please see the data management plan for more information about data access.

Study Oversight

The study will be overseen by the primary investigator, ([name]) and his delegate ([name]) who will ensure data safety protocols are in place and followed by OHRI and CCHC site data handlers. Data safety during reminder testing phase involves the protection of CCHC client identities when sharing data. No identifying information (i.e., name, health card number, address, phone number or email address) will ever be sent to the OHRI team. If a breach were to occur, the study would stop until the breach was resolved and then restart once there is no question of a second breach.

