Those involved in the study will be required to complete a study delegation form.

PROTOCOL NUMBER:	PRINICIPAL INVESTIGATOR (PI):	SITE:
	QUALIFIED INVESTIGATOR (QI): (if different from PI)	
FULL STUDY TITLE	INSTITUTION:	SPONSOR NAME:

Name (N) and Role (R)	Full Signature	Initials	Responsibility (Enter numbers, see list)	Dates of Study Involvement (Y/M/D)	PI/QI Signature to Authorize Delegation of Responsibilities	Date of Signature (Y/M/D)	PI/QI Signature for End of Study or End of Role	Date of PI Signature (Y/M/D)
N				Start				
R]			Stop				
N				Start				
R				Stop				
N				Start				
R				Stop				
N				Start				
R	1			Stop]			
N				Start				
R				Stop				
N				Start				
R	1			Stop	1			

Ethics / Protection of Human Participants

Ethical Standard

The researchers in the current project will uphold the foundational principles of ethical research outlined in the Tri-Council Policy Statement (TCPS2) including *respect for persons*, promoting autonomy through (continued) informed consent, informed decision making about roles in participation, adaptation and accommodation to meet participant needs, *concern for welfare*, where

no unnecessary risk will be imposed on the participant and participants (and their community) will benefit from the participating in the research as well as the outcomes of the research, and *justice*, where participants treated fairly and compensated for their time and recruitment will focus on identifying a representative and diverse sample with specific considerations in place to encourage people from cultural and linguistic minorities and historically underrepresented groups to participate.

Informed Consent Process and Documentation

Consent for trial participation will be waived in accordance with TCPS 2 (Article 3.7A), which permits such waivers when full disclosure would compromise the research objectives, and the study involves no more than minimal risk.

This study evaluates the effectiveness of Behaviour Change Techniques (BCTs) embedded in an electronic reminder to promote diabetic retinopathy screening (DRS) attendance. Obtaining informed consent in advance would introduce bias, as providing study details could alter participants' natural responses to the reminder, undermining internal validity. Additionally, because the study includes a control group, informing all participants could inadvertently serve as a behavioural prompt, contaminating the control condition.

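### Clients are sampled and randomised singly with no check for a shared inbox or household, so a reminder can reach a control; the bias is towards no difference and probably small, and one step at CCHC closes the route

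*Protocol*

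**What the plan says.** The randomisation schedule in the protocol section Control of Bias and Confounding works on individual clients throughout. Step 1 is "330 participants randomly selected from all eligible individuals listed in the Community Diabetes Education Program of Ottawa (CDEPO"). Step 2a is "330 eligible participants randomly assigned to control (n = 165) or intervention (n = 165"). The one constraint on the allocation is step 2b: "Participants control and intervention groups should be balanced across age and date of last chart update".

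Under Participant Inclusion Criteria, item (c), clients must "have consented to virtual communications from CCHC (as indicated by the inclusion of their email address in the CCHC EMR"). Nothing there requires the address to be unique or personal to the client.

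On data flow, the CCHC member responsible for data management "will share a CSV file containing unique client ID codes of all eligible individuals", and OHRI randomises from that file. Study Oversight adds: "No identifying information (i.e., name, health card number, address, phone number or email address) will ever be sent to the OHRI team".

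Informed Consent Process and Documentation gives two reasons for waiving consent. The first is that study details could alter natural responses to the reminder. The second is that "informing all participants could inadvertently serve as a behavioural prompt, contaminating the control condition".

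The protocol nowhere mentions households, relatives, shared e-mail addresses or de-duplication of the eligible list.

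**The concern.** The comparison is a reminder against nothing, so any leak of the reminder into the control arm erodes the contrast directly. The message goes to the contact details on file. If spouses, or a parent and an adult child, are both registered and use one inbox, or simply live together, one can be allocated to the reminder and the other to control. The control may then read the message or hear of it and book. The unique link described under Intervention Phase does not obviously prevent this, since two people can look at one inbox or one landing page.

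The protocol itself regards prompting of controls as harmful, but the schedule leaves this route open. The team that randomises could not close it, because it never receives e-mail or postal addresses. Only CCHC could, and no such task is assigned to it. At stake is an understated intention-to-treat difference and some loss of power.

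**Working it through.** **Inputs from the protocol.** Attendance is 0.03 in control and 0.13 under the reminder, tested two-sided at 5% with pooled variance for 80% power, with 165 per arm randomised (Total Number of Participants and Sites). A total of 250, or 125 per arm, is needed before attrition (Sample Size Determination).

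**The plan's own figure.** With mean proportion 0.08, the pooled-variance formula is

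n = [1.960 × √(2 × 0.08 × 0.92) + 0.842 × √(0.03 × 0.97 + 0.13 × 0.87)]² / 0.10² = 114.3,

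that is 115 per arm, 230 in total. Then 230 / 0.70 = 329, so 330 is reproduced with 30% attrition. The stated 250 is not what 0.03 against 0.13 gives. It is used below only because it is the plan's own analysed sample.

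**Dilution model.** Let c be the share of controls exposed through a relative or shared inbox. Assume that every exposed control responds as if reminded. Then

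control rate = 0.03 + c × 0.10, and difference = 0.13 − control rate.

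The documents do not give c; 2% to 10% is an assumption. Power is the exact binomial power of the uncorrected chi-squared test.

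| c (assumed) | Control rate | Difference (points) | Power, 165 per arm | Power, 125 per arm |
|---|---|---|---|---|
| 0% | 3.0% | 10.0 | 94.0% | 86.2% |
| 2% | 3.2% | 9.8 | 92.7% | 84.1% |
| 5% | 3.5% | 9.5 | 90.4% | 80.7% |
| 10% | 4.0% | 9.0 | 85.8% | 74.6% |

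**How large c could be.** A control is exposed by this route only if the relative is also eligible, is drawn into the 330 and is allocated to the reminder. If a share h of clients has one such eligible relative and the eligible pool is M, then approximately

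c = h × 165 / (M − 1).

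Neither h nor M is in the documents. Some assumed values:

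- h = 20%, M = 330 (no subsampling): 0.20 × 165 / 329 = 10.0%
- h = 10%, M = 500: 0.10 × 165 / 499 = 3.3%
- h = 10%, M = 1,000: 0.10 × 165 / 999 = 1.7%
- h = 5%, M = 2,000: 0.05 × 165 / 1,999 = 0.4%

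Reaching 10% requires both a high sharing rate and a pool hardly larger than the sample. The protocol describes the 330 as a random subsample, so values near or below the bottom of the 2% to 10% range are more plausible.

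**Does correlation within households upset the test?** In a simulation of 330 people, 165 per arm, with 8% attendance and no effect, some people were placed in perfectly concordant pairs and allocated singly. The type I error of the chi-squared test stayed between 0.049 and 0.052 with anything from 0 to 165 pairs. It did not depart from its nominal level.

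**The case against.** Individual randomisation of individually messaged clients is a standard choice, and no statement in the protocol is wrong on its face. The documents do not show that any inbox is shared. Even an exposed control has work to do: Participant Contact and Booking Process requires contact with the screening service, a referral through that person's own primary care provider, and then a scheduled appointment. Full response by every exposed control is therefore a pessimistic assumption, and at 165 per arm power stays above 80% across the whole assumed range. All of this stands, and it limits the point to a cheap improvement.

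A reader might infer three stronger things that the documents do not support.

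- **That consent is waived specifically to protect the controls.** Contamination is the second of two reasons, added after the concern about altered responses, and it refers to informing all participants.
- **That relatives attending together invalidate the chi-squared test.** Allocation is by individual, so correlated outcomes do not disturb the test of no effect, as the simulation shows.
- **That the problem could never be examined afterwards.** The example data file carries no household link, but CCHC keeps the medical record and, under Handling of Participant Withdrawals or Termination, can still match a client to the de-identified record number. It could supply a household flag for a sensitivity analysis without sending identifiers.

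What survives is that the route exists, the protocol regards this kind of prompting as contamination, and nothing in the schedule addresses it.

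**Conclusion.** The point holds as a minor design gap. Sampling and allocation are by individual, an e-mail address need only be on file, and nobody is asked to check for shared contacts, so a reminder can reach a control. The bias is towards no difference.

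Its size rests on an assumed exposure rate and on full response by each exposed control. Under those assumptions the loss is 0.2 to 1.0 percentage points of effect. The power cost is about 1 to 8 points at 165 per arm (94.0% to between 92.7% and 85.8%) and about 2 to 12 points at 125 per arm (86.2% to between 84.1% and 74.6%). Only near the top of the range, and only at 125 per arm, does power drop below the 80% target. With subsampling from a larger pool, the low end or less is the more likely outcome. The case for acting is that prevention is cheap and is best done before allocation.

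**What to change.** Add one sentence ahead of step 1 of the randomisation schedule. Before exporting the ID file, the CCHC data manager flags eligible clients who have the same e-mail address and, where available, the same full address including unit or the same phone number. One client per flagged group is kept at random. Matching on a bare street address should be avoided, because it would remove unrelated residents of one building.

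The check stays inside CCHC, so it respects the rule that no contact details go to OHRI, and it adds one step to an extraction that CCHC already has to run. The cost is a slightly smaller eligible pool and under-sampling of households with more than one registered client, which the trial report should state.
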